#### 5. Background and Rationale: (Describe the research question and justification for undertaking the study explaining the aspects of novelty in the study)

Polycystic ovary syndrome (PCOS) is one of the most common endocrinopathies, affecting approximately 9% to 18% of women in reproductive age. Although the exact pathogenesis of PCOS remains unclear, the characteristic symptoms include oligoanovulation, polycystic ovarian morphology could be explained by hyperandrogenism and hyperestrogenemic not balanced by progesterone. The endocrine, inflammatory, and metabolic changes associated with PCOS have consequences for vision, including neurovascular, metabolic changes in the retina, macular and optic nerve thickness changes.

In recent years it has been discovered that female sex steroids have both systemic and ocular effects, Estrogen, progesterone and androgen receptors have been found in the cornea, lens, iris, ciliary body, retina, lacrimal glands, meibomian glands and conjunctiva, The influence of hormone replacement therapy in menopausal women remains unclear, as some authors support the idea that it improves the quality and the volume of the tear film, whereas others have shown that it increases the risk of dry eye, It's possible that HRT may alleviate postmenopausal dry-eye symptoms by increasing goblet cell density. However, other studies suggest that HRT worsens dry-eye symptoms in some cases, and estrogen-only HRT seems to be worse than a combined estrogen and progesterone therapy.

Reports are stressing on the effect of PCOS on tear film stability rather than amount of the tears denoting the possible effect on meibomian glands (MGs) functions, Loss and morphological deterioration of the MGs are observed in PCOS patients, Yonca Asfuroglu et al. reported that Dry eye was well established in patients with PCOS. They proposed that hyperandrogenism, insulin resistance and subclinical inflammation may be possible contributing factors to the Dry eye spectrum in these patients, They correlated the severity of the Dry eye with the level of inflammation and hyperandrogenism.

*For Treatment of Non-fertility outcomes*, combined oral contraceptive pills (COCs), metformin and anti-androgen drugs are used. COCs are recommended as first-line medical treatment for the management of hyperandrogenism and regulation of menstrual cycles, A study by Chen et al. reported that COCs have no direct

impact on Dry eye, They found no significant differences in Dry eye, as measured by tear osmolarity and ocular surface disease index (OSDI) or Symptom Assessment in Dry Eye (SANDE) questionnaires, between patients taking OCPs and those not taking OCPs. However, results were not conclusive.

Because of the metabolic features of PCOS such as insulin resistance and hyperinsulinemia; insulin-sensitizing agents, especially metformin, have been used as a treatment option for PCOS with OCPS as the second line of treatment. Metformin has a protective effect in diabetic retinopathy, glaucoma, and age related macular degenerations, It can also improves objective measures of Dry Eyes and focus score in Sjögren's Disease.

[figure not shown]
The role of antiandrogens in the treatment of hirsutism in PCOS is controversial; however, there is some weak evidence that flutamide and spironolactone reduce hirsutism. Ilaria Macche et al. found that ocular surface findings are improved by systemic anti-androgen treatment in PCOS and correlate with the severity of the androgen excess-related skin signs.

*For Treatment of Fertility Indications,* Pharmacological options include ovulation induction with clomiphene citrate (CC), letrozole (aromatase inhibitor), metformin, and gonadotrophins; The effect of clomiphene citrate (ovarian stimulant) on vision is minimal; reduction in foveal flicker sensitivity was the only observed visual disturbance.

Although visual disturbance is a possible side effect of aromatase inhibitors use, its incidence is quite variable. Studies found increased tear osmolarity and meibomian gland drop out in women on letrozole with symptomatic dry eye.

## **6. Objectives:** (describe specific objectives or hypotheses behind the study)

The purpose of this study is to prospectively evaluate the ocular surface effects of polycystic ovarian syndrome and different drugs used in its management.

**7. Study Design:** (Please fill in the appropriate study design, see attached PDF guide)

- Descriptive: - Survey (cross sectional)

☐  
☐

- Qualitative

- Analytic: - Observational: - Case-control study

- Cross sectional analytic study

- Cohort (Longitudinal) study

☐  
☐  
☒

- Experimental: - Randomized Clinical Trial

Phase: ☐

- Non-randomized clinical trial

- Animal study

- Cellular study

☐  
☐  
☐

- Others: Please describe:

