**8. Study Methods**

- **Population of study:** (Please provide all details regarding participants including gender, age range and disease conditions. Also indicate if this protocol involves children, prisoners, pregnant women or cognitively impaired or mentally disabled subjects)

Two groups with confirmed laboratory and ultrasonography diagnosis of PCOS , First group will include 30 eyes of 30 females in childbearing period (18-40 years old) scheduled for treatment for non- fertility indications with oral contraceptive pills (as a first line of treatment), and the second group will include 30 eyes of 30 females in childbearing period (18-40 years old) scheduled for treatment with Clomiphene citrate (as a first line of treatment), for fertility indications.

- **Study location:** (Please provide where the study will be conducted and from where study participants will be recruited)

Patients will be recruited from gynecology and dermatology Kasr Al-Ainy clinics and will undergo their ophthalmic examination and investigations at the department of ophthalmology, Kasr Al-Ainy school of medicine.

- **Inclusion criteria:**

1. Females at child bearing period (18-40 years old).
2. Patients recently diagnosed with polycystic ovarian syndrome.

- **Exclusion criteria:**

1. Patients who were diagnosed with Dry eye disease.
2. Patients who were treated with hormonal replacement therapy, Metformin, Aromatase inhibitors, clomiphene citrate or androgen antagonists.
3. Patients who underwent ocular surgeries.
4. Patients with history of diabetes mellitus or hypertension.

- **Methodology in details:**

Two groups with confirmed laboratory and ultrasonography diagnosis of PCOS, First group will include 30 eyes of 30 females in childbearing period (18-40 years old) scheduled for treatment for non- fertility indications with Estradiol valerate / Norgestre tablets for six months, The second group will include 30 eyes of 30 females in childbearing period (18-40 years old) scheduled for treatment with Clomiphene citrate for fertility indications for 6 months.

- Follicle stimulating hormone (FSH), luteinizing hormone (LH) , androgen, estrogen, progesterone , fasting insulin and neutrophil to lymphocyte ratio (NLR) will be obtained.
- The two groups will undergo complete ophthalmic examination including :

\*Full history.

\*Standard Patient Evaluation of Eye Dryness Questionnaire (SPEED) in order to quickly track the progression of dry eye symptoms over time.

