### 9- Study outcomes:

- **Primary outcomes** (Most important measurable outcomes)
  - 1- Measuring changes in meibomian glands function, break up time, tear meniscus height, and lipid layer thickness in polycystic ovarian syndrome and with different drugs used in managing it.
- **Secondary outcome parameters** (other outcomes to be assessed)
  - 1- Measuring eye lid margin, conjunctival hyperemia, and ocular surface staining in polycystic ovarian syndrome and with different drugs used in managing it.
  - 2- Measuring the central corneal thickness (CCT) changes in polycystic ovarian syndrome and with different drugs used in managing it.

**10- Sample size** (number of study subjects included and justification including the clinical and statistical assumptions supporting sample size calculation)

$$\left( \frac{Z_{a/2} + Z_B}{P_1 - P_2} \right)^2 (p_1 q_1 + p_2 q_2)$$

(Takazawa & Morita, 2020)

n = sample size

Z a/2 (The critical value that divides the central 95% of the Z distribution)

ZB (The critical value that divides the central 20% of the Z distribution)

p1 = prevalence in case group

p2 = prevalence in control group.

q = 1-p

Epi Info STATCALC was used to calculate the sample size by considering the following assumptions:- 95% two-sided confidence level, with a power of 80%. &  $\alpha$  error of 10% . The final maximum sample size taken from the Epi- Info output was 26. Thus, the sample size was increased to 30 subjects with total 30 eyes in each group to assume any drop out cases during follow up.

[figure not shown]
**11- Statistical analysis** (Please describe your data analysis plan)

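### The objective and outcomes claim to evaluate the ocular surface effects of PCOS, but every participant has PCOS, so no such effect can be estimated

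*Combined protocol and SAP*

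**What the plan says.** - **Objective (section 6).** The study will prospectively "evaluate the ocular surface effects of polycystic ovarian syndrome and different drugs used in its management". This is two questions: one about the disease and one about the drugs.
- **Design (section 7).** The ticked box appears to be "Cohort (Longitudinal) study". The layout of the boxes is broken in the text available, but the case-control box does not appear to be ticked.
- **Participants (section 8).** The second inclusion criterion is "Patients recently diagnosed with polycystic ovarian syndrome". The study has "Two groups with confirmed laboratory and ultrasonography diagnosis of PCOS": 30 women starting an oral contraceptive for non-fertility indications, and 30 "scheduled for treatment with Clomiphene citrate for fertility indications for 6 months". The first exclusion is "Patients who were diagnosed with Dry eye disease". Examinations take place before treatment, at 3 months and at the end of the course.
- **Outcomes (section 9).** The primary outcome ends with "lipid layer thickness in polycystic ovarian syndrome and with different drugs used in managing it". Both secondary outcomes use the same two-part form.
- **Sample size (section 10).** The formula's legend defines p1 as the prevalence among cases and has "p2 = prevalence in control group". No value is given for either.
- **Analysis (section 11).** The two groups are compared with t-tests or Mann-Whitney tests, and repeated measures ANOVA is used within and between groups over visits. No other group or reference population is mentioned.

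**The concern.** An effect of having PCOS is a contrast between women with it and comparable women without it. The plan promises that contrast in its objective and in every listed outcome, but neither recruitment nor analysis provides it. Half of the stated purpose therefore has no data behind it, and no later analysis of the 60 women can supply them. A published statement on what PCOS does to the ocular surface would rest on a description of affected women alone.

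The drug question has a related limit. There is no untreated PCOS group, and treatment is assigned by indication. Neither the change within a group nor the difference between groups isolates a drug effect, and section 11 does not say so.

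**Working it through.** **1. Can the PCOS effect be estimated?** Write an outcome as Y = μ + β·P + (treatment group and visit terms) + error, where P = 1 for PCOS and 0 otherwise. By the inclusion criterion P = 1 for all 60 women, so μ and β enter only as the sum μ + β and cannot be separated. Equivalently, the standard error of a PCOS contrast is σ√(1/n₁ + 1/n₀). With n₁ = 60 and n₀ = 0 it is undefined, and increasing n₁ does not help.

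**2. What the planned comparisons do estimate.**

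| Planned quantity | What it contains |
|---|---|
| Baseline values | Description of untreated PCOS women who meet the criteria |
| Within-group change | Drug + time + disease course |
| Between-group difference in change | Drug difference + anything else that differs between women treated for fertility and for non-fertility reasons |

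No row contains the effect of PCOS. In the third row, drift common to both groups cancels, but differences tied to indication do not.

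**3. The plan's own figure.** Section 10 reports n = 26, raised to 30 for dropout. The formula is n = ((Z₁ + Z₂)/(p1 − p2))² × (p1q1 + p2q2), with Z₁ the critical value for alpha and Z₂ that for power. Since p1 and p2 are not stated, 26 can be neither reproduced nor refuted. Back-solving at 80% power shows what it would need, with p2 assumed:

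| Two-sided alpha | p2 = 0.10 | p2 = 0.50 |
|---|---|---|
| 0.05 | p1 ≈ 0.42 | p1 ≈ 0.84 |
| 0.10 | p1 ≈ 0.38 | p1 ≈ 0.81 |

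Check of one cell: (1.960 + 0.842)² = 7.85, and 7.85 × (0.42×0.58 + 0.10×0.90)/(0.32)² = 7.85 × 0.3336/0.1024 = 25.6, which rounds up to 26. Both alphas are shown because section 10 gives both a 95% confidence level and a 10% alpha error. The calculation gives no means of telling which groups the two prevalences belong to.

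**4. What the dry-eye exclusion does (illustration).** Suppose the exclusion removed exactly the worst fraction q of PCOS women on a normally distributed measure. The mean of those remaining would look better by φ(z)/(1 − q), where z is the cut-off:

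- q = 0.1: 0.195 SD
- q = 0.2: 0.350 SD
- q = 0.3: 0.497 SD

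The values of q are assumptions; the documents give none. If the diagnosis rested on an earlier measurement, the shift seen at baseline is reliability × these values. With reliability assumed at 0.5 to 0.7, that is 0.5 × 0.195 = 0.10 to 0.7 × 0.497 = 0.35 SD. It would be smaller again because a clinical diagnosis is not a clean cut on one measure. Step 1 does not depend on any of this.

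**The case against.** **The wording may mean only a description of PCOS women at baseline.** That is a reasonable intention and the design can deliver it. But the objective speaks of effects, so the text should be changed to say what is meant.

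**Other information might stand in for a control group.** Section 8 calls a congestion severity above two abnormal, so abnormality at baseline can be described for that sign. It is a secondary outcome, no cut-off is given for the primary measures, and no comparison with norms is planned. Hormone levels are collected, but section 11 plans no correlation or regression, and a gradient within PCOS would still not be the effect of having PCOS.

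**The case and control labels may be generic formula text.** This stands. They show a mismatch with the enrolled groups but do not prove that a case-control comparison was intended.

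**The exclusion is defensible.** For the drug question it gives a cleaner starting point, and narrowing it is a trade-off. It covers women already diagnosed, so undiagnosed dry eye can still enter and be measured.

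**Stronger readings that the documents do not support.** A reader might infer that the exclusion makes later visits look worse through regression to the mean, and that this would be credited to the drugs. The usual expression, shift × (1 − reliability), needs selection on the same measurement that serves as baseline. The criterion refers to a past diagnosis, and no cut-off at the baseline visit is stated. With stable true values and independent errors, the regression has already happened by baseline and the expected drift from this source is zero. A reader might also infer that the results must lean towards little effect of PCOS. That direction needs a comparator outside the study, and none is specified.

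**Conclusion.** The point holds for the missing comparator. It follows from the objective, eligibility, outcomes and analysis sections read together and rests on no numerical assumption: the PCOS effect is not estimable, whatever the number enrolled. The absence of women without PCOS is sufficient by itself.

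The dry-eye exclusion is a separate and lesser matter. It restricts the population to which the baseline description applies. The possible shift of 0.10 to 0.50 SD, taking both cases illustrated, is conditional on the assumed fractions and reliability and is not an estimate for this study.

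It would be too strong to call the whole study uninformative. The two-drug comparison does not need a non-PCOS group. It can be reported as a non-randomised association, and change within each group can be described without attributing it to the drug alone.

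**What to change.** - **Sections 6 and 9.** Replace the reference to effects of PCOS with: *ocular surface status before treatment, and change during treatment, in women with PCOS without a prior dry-eye diagnosis*. State that no conclusion will be drawn about the effect of PCOS itself.
- **Section 10.** Redefine p1 and p2 as the two treatment groups actually compared. Deleting the control-group label alone would leave p2 undefined. Whether 26 suits that contrast can be checked only once the two assumed values are stated.
- **Section 11.** State that within-group change has no untreated comparator and cannot be attributed to the drug alone. Report the between-group difference in change as a non-randomised association subject to confounding by indication (fertility versus non-fertility).

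**Cost:** wording in sections 6, 9, 10 and 11, and a narrower claim. These edits add no patients or visits, and the exclusion can stay as written.

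Keeping the disease question instead would require women without PCOS, examined in the same way, and a fresh look at the dry-eye exclusion. For scale, with one added group of 30 (assumed), two-sided alpha 0.05 and 80% power, the detectable difference against all 60 PCOS women is 2.80 × √(1/60 + 1/30) = 0.63 SD. That is a larger study and is not needed for the correction above.

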**8. Study Methods**

- **Population of study:** (Please provide all details regarding participants including gender, age range and disease conditions. Also indicate if this protocol involves children, prisoners, pregnant women or cognitively impaired or mentally disabled subjects)

Two groups with confirmed laboratory and ultrasonography diagnosis of PCOS , First group will include 30 eyes of 30 females in childbearing period (18-40 years old) scheduled for treatment for non- fertility indications with oral contraceptive pills (as a first line of treatment), and the second group will include 30 eyes of 30 females in childbearing period (18-40 years old) scheduled for treatment with Clomiphene citrate (as a first line of treatment), for fertility indications.

- **Study location:** (Please provide where the study will be conducted and from where study participants will be recruited)

Patients will be recruited from gynecology and dermatology Kasr Al-Ainy clinics and will undergo their ophthalmic examination and investigations at the department of ophthalmology, Kasr Al-Ainy school of medicine.

- **Inclusion criteria:**

1. Females at child bearing period (18-40 years old).
2. Patients recently diagnosed with polycystic ovarian syndrome.

- **Exclusion criteria:**

1. Patients who were diagnosed with Dry eye disease.
2. Patients who were treated with hormonal replacement therapy, Metformin, Aromatase inhibitors, clomiphene citrate or androgen antagonists.
3. Patients who underwent ocular surgeries.
4. Patients with history of diabetes mellitus or hypertension.

- **Methodology in details:**

Two groups with confirmed laboratory and ultrasonography diagnosis of PCOS, First group will include 30 eyes of 30 females in childbearing period (18-40 years old) scheduled for treatment for non- fertility indications with Estradiol valerate / Norgestre tablets for six months, The second group will include 30 eyes of 30 females in childbearing period (18-40 years old) scheduled for treatment with Clomiphene citrate for fertility indications for 6 months.

- Follicle stimulating hormone (FSH), luteinizing hormone (LH) , androgen, estrogen, progesterone , fasting insulin and neutrophil to lymphocyte ratio (NLR) will be obtained.
- The two groups will undergo complete ophthalmic examination including :

\*Full history.

\*Standard Patient Evaluation of Eye Dryness Questionnaire (SPEED) in order to quickly track the progression of dry eye symptoms over time.

\*Manifest refraction.

\* Corrected distance visual acuity.

\* Anterior segment examination using slit lamp, Schirmer's test and tear film breakup time test.

\* Fundus examination.

\* Measuring central corneal thickness (CCT) using Corneal pachymetry.

•Beside Schirmer's test, tear film breakup time test and fluorescein break-up patterns, Dry eye assessment will be performed using Dry Eye Diagnostic System device (D130, Medi-Works Precision Instruments; Shanghai, China). Device to have a Dry eye diagnosis brings out an automatic result of non-invasive break up test (NIBUT) and tear meniscus height after taking one video. It is a fully automatic analysis system to provide efficient quantified evaluation for the overall stability of the tear film. Also it uses identification system that depicts the tear meniscus area and measures the tear height automatically.

The device also automatically analyses the meibomian glands, lipid layer thickness, and eyelid margin. The built-in infrared lighting system helps to obtain the enormous image scope of the meibomian glands. Finally the device identifies and calculates percentages of

conjunctival congestion and ciliary congestion, Thus evaluating the severity of eye congestion. If the degree of severity of eye congestion is more than two, it is abnormal.  
\*Examination and laboratory tests will be done before, 3 months after starting treatment and after finishing the treatment course.

- **Intervention:**

☒ Diagnostic intervention (please describe):

Imaging ocular surface using dry eye diagnostic system.

☐ Therapeutic intervention (please describe):

☐ No intervention

- **Does the research involve?**

☒ Human participants

☐ Biological samples/Tissues

☐ Identifiable private data/Information

- **Type of consent of study participants:**

☒ Written consent

[figure not shown]
☐ Oral consent

☐ No consent needed (Please justify)

- **Potential risks:**

(Please mention all risks involved even mild ones as pain, discomfort, chance of infection or psychological effects)

1- No possible risks

- **Confidentiality of data:** (Please explain how privacy and confidentiality of data and records will be maintained)
- Names and private data of patients will not be published, only the results of the study will be analyzed and published.

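### Recruiting from both gynecology and dermatology clinics, with clinic not listed as data and no adjustment planned, leaves a risk that the comparison of pill and clomiphene partly reflects referral source

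*Combined protocol and SAP*

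**What the plan says.** The study is an observational cohort (section 7). On where the women come from, section 8 (Study location) says: "Patients will be recruited from gynecology and dermatology Kasr Al-Ainy clinics". It gives no share for either clinic and does not tie a clinic to a group.

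The groups are defined by indication, 30 women each. The first is "scheduled for treatment for non- fertility indications with oral contraceptive pills (as a first line of treatment"; the second is "scheduled for treatment with Clomiphene citrate (as a first line of treatment), for fertility indications".

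Section 5 supplies the link to the outcomes. It reports that "ocular surface findings are improved by systemic anti-androgen treatment in PCOS and correlate with the severity of the androgen excess-related skin signs", and of another study that "They correlated the severity of the Dry eye with the level of inflammation and hyperandrogenism". It also gives two reasons for using the pill: "COCs are recommended as first-line medical treatment for the management of hyperandrogenism and regulation of menstrual cycles".

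The data listed in section 8 include serum androgen, the neutrophil to lymphocyte ratio (NLR), a full history and the eye measurements, with examinations and laboratory tests before treatment, at 3 months and at the end of the course. The recruiting clinic and a skin-sign score are not listed. Section 11 plans a t-test or Mann-Whitney test between groups and a repeated measures ANOVA across visits. It names no covariate, matching or stratification.

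**The concern.** A woman who attends dermatology for PCOS most plausibly does so for a skin complaint, which is a non-fertility indication. Women starting clomiphene for fertility would more plausibly come through gynecology. If so, the second clinic is a route into the study that is open mainly to one group, and it selects on a feature that the protocol itself relates to the ocular surface.

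The between-drug comparison is at stake. A difference in tear film or meibomian gland measures at a visit could come partly from who was referred, not from what they took. Because clinic and skin-sign severity are not among the listed data, a reader of the results could not check how far this had happened.

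**Working it through.** **1. What the documents fix and what they leave open.** Fixed: two recruiting clinics, grouping by indication, 30 women per group, a two-sided 5% level, and a reported correlation between skin-sign severity and ocular findings. Open: the dermatology share of either group, any difference between clinics in the outcomes, and the size of that correlation. The plan has no figure of its own to reproduce on this point.

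**2. Size of the bias in a single-visit comparison.** All inputs below except the group size and the 5% level are assumptions. If a share *s* of the pill group comes from dermatology, the clomiphene group comes wholly from gynecology, and dermatology women differ by *d* SD on an outcome, then

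bias = *s* × *d* (in SD).

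For a t-test with 30 per group there are 58 degrees of freedom, and the noncentrality is bias ÷ √(1/30 + 1/30) = bias × √15. The chance of a two-sided p < 0.05 with no drug difference is then:

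| Share *s* | Difference *d* (SD) | Bias (SD) | Noncentrality | False-positive rate |
|---|---|---|---|---|
| 0.25 | 0.3 | 0.075 | 0.29 | 5.9% |
| 0.5 | 0.3 | 0.15 | 0.58 | 8.8% |
| 0.5 | 0.5 | 0.25 | 0.97 | 15.9% |
| 0.7 | 0.5 | 0.35 | 1.36 | 26.6% |
| 0.5 | 0.8 | 0.40 | 1.55 | 33.2% |

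**3. The same question built from skin severity.** Suppose dermatology women have skin severity higher by *D* SD, and severity correlates *r* with the outcome. Then bias = *s* × *D* × *r*. With *s* from 0.25 to 0.75, *D* from 0.5 to 1.0 and *r* from 0.2 to 0.5 (all assumed), the bias runs from 0.25 × 0.5 × 0.2 = 0.025 SD to 0.75 × 1.0 × 0.5 = 0.375 SD. The false-positive rate (normal approximation) runs from 5.1% to 30.6%. At the low end the problem is negligible.

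**4. Change over time.** The primary outcome in section 9 is change. If the clinic difference is the same at every visit, it is subtracted out of each woman's change, and the group-by-visit comparison is unaffected. If women with more severe skin signs respond differently, the part *s* × (difference in response) stays in the comparison. The documents give nothing from which to size that part.

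**5. Cost of restricting to gynecology.** With half the pill group from dermatology, a comparison limited to gynecology has 15 against 30. The difference detectable with 80% power (two-sided 5%, t-test) rises from 0.74 SD at 30 against 30 to 0.91 SD, and power for the former difference falls from 80% to 62%. With 70% from dermatology (9 against 30) the figures are 1.09 SD and 47%.

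**The case against.** The strongest objection is that enrichment is inferred. A reader might conclude that the pill group *is* enriched for skin disease, or even drawn wholly from dermatology. The documents do not support that: they map neither clinic to a group, and cycle regulation is also a stated reason for the pill, so the group need not be skin-led. This stands, and the point is therefore worded as a risk.

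A reader might also infer that adjustment with the planned data can do nothing. That goes too far. Baseline eye measurements, serum androgen and NLR are all collected, so partial adjustment is possible, although serum androgen is not skin-sign severity. A full history is also taken and might capture some of the missing information, but neither clinic nor skin severity is named.

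The false-positive rates apply only to level comparisons at one visit, whereas the primary outcome is change. This limits the size of the claim. It does not remove the claim, because section 11 also plans between-group tests and because response may differ.

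Recruiting only from gynecology would not make the groups comparable. The pill is described as first-line for hyperandrogenism, so women starting it in gynecology may also be selected for androgen excess. This stands: clinic is only one part of confounding by indication.

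Finally, the clinic mix does not bias the pill group's own change, since each woman is compared with her own baseline. It affects only to whom that result applies. Excluding diagnosed dry eye and previous users of androgen antagonists may narrow baseline differences, but undiagnosed variation in tear and gland measures remains.

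**Conclusion.** The point holds as an unaddressed risk of confounding by referral source, within the wider confounding by indication. It rests on one inference, that dermatology referrals go mainly to the pill group, and on the protocol's own summary of a correlation for which it gives no effect size. Under the assumptions shown, the false-positive rate of an unadjusted single-visit test runs from about 5% to about 33%. The documents cannot say where in that range the study would fall. The group-by-visit comparison is affected only if response differs by skin severity or clinic. The planned data allow partial adjustment, but none is specified, and without the clinic recorded the mix could not be shown. The remedy is cheap and worth making before recruitment.

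**What to change.** - **Section 8, Study location:** recruit both groups from the gynecology clinics where feasible. Otherwise record the recruiting clinic for every woman and report it by treatment group.
- **Section 11:** adjust the between-drug comparison for the baseline value of the outcome and for baseline androgen, both already collected. Use the pre-treatment androgen value, since later values may be altered by treatment. If dermatology recruits are included, repeat the comparison among gynecology-recruited women as a sensitivity analysis. Do not make that restricted comparison the main analysis, given its loss of power.
- **Interpretation:** state that confounding by indication remains under either recruitment option, so between-drug differences are associations.

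The cost is one extra field, one extra analysis with lower precision and, if recruitment is confined to gynecology, possibly slower filling of the pill group.
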